2.2.3 Toxicology Studies

Eli Lilly and Company has performed toxicology studies in rodents and dogs. Details of each of these studies can be found in the Investigator Brochure.

In 6-month long-term nonclinical toxicity studies, daily dosing of LY2157299 resulted in dose-progressive incidence of vascular degeneration to the base of the aorta in dogs and rats. Vascular changes led to transmural aneurysms and mortality in mid-high dose-treated rats. Due to the possibility of aneurysm formation, patients with a history of or predisposition of developing aneurysms should not receive LY2157299. Subsequent cardiovascular function studies carried

out in dogs revealed that LY2157299 can cause a decrease in blood pressure and increases in heart rate and arterial pulse pressure, all reversible. There were no compound-attributable changes in QT intervals, arrhythmias, or altered waveforms noted. Because of the associated cardiac events in animal studies, patients on LY215799 undergo cardiac monitoring, including assessment of heart rate, blood pressure and cardiac functions. Regular monitoring of biomarkers for cardiac events, including troponin-I, B type natriuretic peptide and high sensitivity C-reactive protein is required..TGF- β is an important immunomodulator, hence, careful monitoring of immune functions and infection rates is important. Because LY2157299 inhibits TGF- β receptor type-1 kinase, an autoimmune reaction may occur. To date, no clinically significant immune reactions have been reported or observed up to doses of 300 mg/day in a 14 days-on / 14 days-off treatment regimen.

LY2157299 should not be administered to pregnant patients or all efforts should be made to prevent pregnancy due to TGF- β 's role in embryogenesis. Literature searches as well as treatment with LY2157299 in pregnant rats showed increased resorptions and alterations in fetal skeletal morphology at dose equivalents of 300 mg/day in humans.

LY2157299 does not demonstrate any direct bone marrow toxicity in either animal studies with continuous dosing for 6 months, nor in human colony-forming unit studies with human bone marrow progenitor cells. There have been 2 cases with drug-related severe thrombocytopenia and associated pan-cytopenia observed, but they cannot be explained at this juncture.

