3.2 Inclusion Criteria

- 3.2.1 Biopsy proven breast carcinoma which is persistent and metastatic or recurrent and metastatic.
- 3.2.2 Patients must have failed at least one line of chemotherapy for metastatic disease.
- 3.2.3 Patients who are HER2+ as defined by ASCO CAP guidelines must have failed all prior therapy known to confer clinical benefit
- 3.2.4 Patients must have at least 3 distinct metastatic sites with at least one measurable lesion which is at least 1 cm or larger in largest diameter.
- 3.2.5 At the time of enrollment, patients must be ≥ 4 weeks[‡] since all of the following treatments (and recovered from the toxicity of prior treatment to \leq Grade 1, exclusive of alopecia):
 - major surgery;
 - radiotherapy;
 - chemotherapy (note: must be ≥ 6 weeks since therapy if treated with a nitrosourea, mitomycin, or monoclonal antibodies such as bevacizumab);
 - immunotherapy;
 - Biotherapy/targeted therapies.
([‡] - Patients can begin two weeks from prior treatment if they are asymptomatic from previous therapy)
- 3.2.6 Patient ≥ 18 years of age.
- 3.2.7 Patient life expectancy > 6 months.
- 3.2.8 ECOG status of 0 or 1
- 3.2.9 Adequate organ function including:
 - a) Marrow: Hemoglobin ≥ 10.0 g/dL, absolute neutrophil count (ANC) $\geq 1,500/\text{mm}^3$, and platelets $\geq 100,000/\text{mm}^3$.
 - b) Hepatic: Serum total bilirubin $\leq 1.5 \times$ upper limit of normal (ULN)
(Patients with Gilbert's Disease may be included if their total bilirubin is ≤ 3.0 mg/dL), alanine aminotransferase (ALT), and aspartate aminotransferase (AST) $\leq 2.5 \times$ ULN. If the patient has known liver metastases, an ALT and/or AST $\leq 5 \times$ ULN are allowed.
 - c) Renal: Estimated or measured creatinine clearance ≥ 60 mL/min.
 - d) Other: Prothrombin time (PT) and partial thromboplastin time (PTT) $<$ ULN.
- 3.2.10 Patients must have negative tests (antibody and/or antigen) for hepatitis

viruses B and C unless the result is consistent with prior vaccination or prior infection with full recovery.

- 3.2.11 Male and female patients of child-producing potential must agree to use effective contraception while enrolled on study and receiving the experimental drug, and for at least 3 months after the last treatment.
- 3.2.12 Ability to understand and the willingness to sign a written informed consent document. Patients may not be consented by a durable power of attorney.

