 - d) have predisposing conditions that are consistent with development of aneurysms of the ascending aorta or aortic stress (for example, family history of aneurysms, Marfan-Syndrome, bicuspid aortic valve, evidence of damage to the large vessels of the heart documented by computed tomography (CT) scan with contrast).
- 3.3.9 Troponin I above ULN,
- 3.3.10 Patients with a remote history of asthma or active mild asthma may participate.
- 3.3.11 Active infection, including unexplained fever (temperature > 38.5°C).
- 3.3.12 Systemic autoimmune disease (e.g., systemic lupus erythematosus, active rheumatoid arthritis, Marfan Syndrome, etc.).
- 3.3.13 A known allergy to any component of LY2157299.
- 3.3.14 Patients who, in the opinion of the Investigator, have significant medical or psychosocial problems that warrant exclusion. Examples of significant problems include, but are not limited to:
- a) Other serious non-malignancy-associated medical conditions that may be expected to limit life expectancy or significantly increase the risk of SAEs.

b) Any condition, psychiatric, substance abuse, or otherwise, that, in the opinion of the Investigator, would preclude informed consent, consistent follow-up, or compliance with any aspect of the study

3.3.15 Pregnant or nursing women, due to the unknown effects of LY2157299 on the developing fetus or newborn infant.

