5. TREATMENT PLAN

5.1 Investigational Agent or Device Administration

Enrolled patients will receive 300 mg/day of LY2157299. LY2157299 will be administered as an oral drug tablet.

The study drug will be administered orally on a 28-day cycle (1 cycle=28 days), every 2 weeks, or 14 days on / 14 days off. Blood samples will be obtained at baseline, and weeks 2, 6 and 15 for immune monitoring. Imaging by PET/CT or CT(Chest/Abdomen/Pelvis) will be performed at baseline, 5 weeks and 15 weeks. The chosen metastatic sites will receive conformal external beam radiation 7.5 Gy/fraction x 3, to a total of 22.5 Gy over the course of one week (on alternating days):

- lesion 1 will be irradiated at week 1 (RT starts 1 day after 1st dose of LY2157299),
- lesion 2 will be irradiated at week 5 (RT starts after 1stdose of the second cycle of LY2157299)

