5.2 Pretreatment Evaluations

Screening and Baseline Evaluations/Procedures

These evaluations will be carefully reviewed to determine the patient's eligibility for the study (see study calendar, section 5.10).

1. Signed, written informed consent: Consent must be completed prior to performing any study-related procedures
2. Complete physical examination including height, weight and full skin exam.

3. Medical history: Detailed documentation of demographics, disease and treatment history with outcomes.
4. ECOG performance status assessment.
5. Concurrent medications.
6. Echo / Doppler.
7. Hematology: CBC with differential and platelet count and peripheral blood smear. Coagulation (PT/INR, PTT); Serum chemistries: Electrolytes (sodium, potassium, chloride, and bicarbonate), blood urea nitrogen (BUN), creatinine, glucose, and liver function tests (aspartate aminotransferase (AST) and/or alanine aminotransferase (ALT), alkaline phosphatase (ALP), total bilirubin, lactate dehydrogenase (LDH), and Troponin I..
8. Tumor measurement at baseline by PET/CT or CT(chest/abdomen/pelvis).
9. MRI or Brain CT with contrast is required at baseline
10. Stool fecal occult blood test of 2 consecutive samples: if patients have positive fecal occult blood, full GI workup will be conducted and patients will be excluded if active bleeding is detected.
11. LY2157299 Serum pregnancy test for women of childbearing age.

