5.3 On-Study Evaluations

(See study calendar, section 5.10)

1. Physical exam: including complete skin evaluation and evaluation of oral mucosa prior to start of **each** RT cycle and **prior** to each LY2157299 administration.
2. Hematology: CBC with differential and platelet count and peripheral blood smear. PT/INR,PTT should be evaluated following multiple doses of LY2157299; Serum chemistries: Electrolytes (sodium, potassium, chloride, and bicarbonate), BUN, creatinine, glucose, and liver function tests (AST, ALT, ALP, total bilirubin, LDH, and Troponin I C). These will be carried out prior to start of each RT cycle and prior to each cycle of 2 weeks of BID LY2157299 administration.
3. ECHO/Doppler : Week 8 within 5 days prior to starting week 9 LY2157299 administration and Week 15
4. Study Special Tests: TGF β levels (at wk 1 day -1 and week 15 visit), immune evaluation at weeks 1 day -1, 2, 5 and 15 LY2157299 PK (pre- & after completion of drug cycle day 14 & at day 42).
5. Tumor measurement by PET/CT/ CT(chest/abdomen/pelvis) at weeks 5 and 15.
6. Adverse events evaluated and recorded using the NCI CTCAE version 4.0 throughout the treatment period (weeks 0-15).

To date, LY2157299 at the planned dose for this study is well tolerated in patients. If a toxicity is observed, a dose reduction may be considered based on the aggregate safety information of LY2157299, if other plausible reasons for a toxicity have been excluded.

Specifically, no bone marrow toxicities were detected in nonclinical toxicology studies; 1 toxicity was reported in a patient with glioblastoma in whom a Grade 4 thrombocytopenia was observed and this toxicity was potentially associated with administration of LY2157299 monotherapy. If a similar case occurs, the drug should be discontinued until platelet counts either return to Grade 1 or baseline.

If a patient experiences any of the following events that are considered possibly related to LY2157299 and not to study disease, LY2157299 will be omitted until the event resolves:

- Grade 4 Thrombocytopenia
- Grade 3 thrombocytopenia associated with bleeding
- Grade 4 Anemia
- absolute neutrophil count (ANC) $<0.5 \times 10^9/L$ for longer than 7 days, or ANC $<1.0 \times 10^9/L$ with a single temperature of $>101^{\circ}\text{F}/38.3^{\circ}\text{C}$ or a sustained temperature of $>100.4^{\circ}\text{F}/38^{\circ}\text{C}$ for more than 1 hour, or platelet count $<25,000 \times 10^9/L$

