5.10 Study Calendar

	Pre-Study	Wk 1 (Day -1) 0	Wk 1 (Day +1) (+/- 3 days)	Wk 2 (+/- 3 days)	Wk 3 (+/- 3 days)	Wk 4 (+/- 8 days)	Wk 5 (+/- 3 days)	Wk 6 (+/- 3 days)	Wk 7 (+/- 3 days)	Wk 8 (+/- 3 days)	Wk 9 (+/- 8 days)	Wk 10 (+/- 3 days)	Wk 11 (+/- 3 days)	Wk 12 (+/- 3 days)	Wk 13 (+/- 3 days)	Wk 14 (+/- 3 days)	Wk 15 (+/- 8 days)	Follow-up
Investigational Agent LY2157299^a			X	X ^{a,d}			X	X ^{a,d}			X ^{a,d}	X ^{a,d}			X ^{a,d}	X ^{a,d}		
RT				X ^d				X ^d										
Informed consent	X																	
Demographics	X																	
Medical history	X																	
EKG ^b	X ^b																	
Concurrent meds	X			X-----										X				
B-HCG ^c	X ^c																	
Performance status	X	X		X		X		X						X		X ^d	X	
Physical exam ^d (Vital signs)	X ^d	X ^d		X ^d		X ^d		X ^d		X ^d		X ^d		X ^d		X ^d	X	
CBC w/diff, plts, Serum chemistry ^e CEA/CA 27.29 ^f	X ^{e,f}	X ^e		X ^e	X ^e		X ^f	X ^e		X ^e	X ^e			X ^e		X ^{e,f}		
PT/INR/PTT	X	X		X	X			X		X	X			X			X	
Hepatitis B and C HbSAG, HCV Ab (antibody and/or antigen)	X																	

IND # 126952

Stool fecal occult blood test (2 consecutive)	X															
Adverse event evaluation			X-----											X		
PET/CT/CT(CAP)	X						X								X	
MRI or Brain CT with contrast	X															
Tumor tissue for TBRS signature	X ^g															
Blood draw for VEGF		X		X			X								X	
Blood draw for immunological studies		X		X			X								X	
Blood draw (pre and post) for LY2157299 pK		X								X						
Blood draw for LY2157299 cardiotoxicity (Troponin I)	X	X				X			X			X			X	
Echo/Doppler	X								X					X	X	
a: LY2157299 Administration of investigational drug is given 14 days on and 14 off. B: Before 1 st RT & repeated during the study if indicated. C: Serum pregnancy test (women of childbearing potential). D: PE must include full vital signs, skin and oral mucosa exam and prior to each LY2157299 administration and each RT cycle. PE continue monthly for the first 3 months following therapy then yearly for 5 years. E: Albumin, alkaline phosphatase, total bilirubin, bicarbonate, BUN, calcium, chloride, creatinine, glucose, LDH, phosphorus, potassium, total protein, SGOT[AST], SGPT[ALT], sodium f. CEA/CA 27.29 if elevated at baseline will be repeated at weeks 5 and 15. g. Archival tissue.																

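### No pregnancy test is scheduled before drug courses 2, 3 and 4, although section 2.2.3 reports fetal harm in rats at the equivalent of the trial dose

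*Combined protocol and SAP*

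**What the plan says.** **Hazard.** Section 2.2.3 says "LY2157299 should not be administered to pregnant patients or all efforts should be made to prevent pregnancy". It gives the reason: treated pregnant rats showed "increased resorptions and alterations in fetal skeletal morphology at dose equivalents of 300 mg/day in humans". Sections 5.1 and 7 set the trial dose at 300 mg/day, so the protocol states no margin between the two.

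**Safeguards in place.**
- 3.3.15 excludes "Pregnant or nursing women, due to the unknown effects of LY2157299 on the developing fetus or newborn infant".
- 3.2.11 says that patients who could conceive or father a child "must agree to use effective contraception while enrolled on study and receiving the experimental drug", and for at least 3 months after the last treatment.
- 5.2 item 11 lists, among the screening and baseline evaluations, a "Serum pregnancy test for women of childbearing age".
- 5.3 item 1 and note D of the 5.10 calendar require a physical exam before LY2157299 is given and before each radiotherapy cycle.
- 5.7 lists pregnancy as a ground for stopping treatment while follow-up continues, and asks that the pregnancy and any exposed infant be followed.
- 8.3 requires the drug supplier to be told of pregnancies in exposed patients.

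**Schedule.** Section 5.1 says "The study drug will be administered orally on a 28-day cycle", with 14 days on and 14 days off. The 5.10 calendar marks drug at weeks 1-2, 5-6, 9-10 and 13-14. Section 5.3 item 2 requires hematology, coagulation and chemistry before each two-week drug course and names no pregnancy test.

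**The concern.** The plan names a fetal hazard at the equivalent of its own dose, tests for pregnancy once, and then gives three more courses. Contraception lowers the chance of a pregnancy but does not reveal one. Removal under 5.7 and reporting under 8.3 operate only once a pregnancy is known. A site that follows the plan exactly could therefore start a further 14-day course in a woman who conceived after screening and does not yet know it.

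The plan handles its other animal-derived hazard differently. For cardiac toxicity it repeats troponin I during treatment and ties an on-study echocardiogram to a course start, "within 5 days prior to starting week 9 LY2157299 administration". Nothing comparable is scheduled for pregnancy.

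What is at stake is fetal exposure that could have been avoided. The trial's efficacy conclusions do not depend on it.

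**Working it through.** The plan gives no figure of its own on this point. The check is a reading of the schedule and a count of days.

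**1. Scheduled tests.**
- 5.2 item 11: one serum test at screening or baseline, with no stated interval before the first dose.
- 5.10, B-HCG row: one mark, in the Pre-Study column.
- 5.3: none.

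The three places agree, so the single calendar mark does not look like a table-extraction fault. The calendar notes need care, because they run together: "repeated during the study if indicated. C: Serum pregnancy test (women of childbearing potential". The words about repeating belong to note B, which is attached to the EKG row. Only the words from the letter C onward concern the pregnancy test, and they provide for no repeat.

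**2. Course starts.** With 28-day cycles, course k starts on day 1 + 28 × (k − 1).

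**3. Age of the screening result.** Measured from the start of course 1, the result is at least 28 × (k − 1) days old when course k starts. The unstated time from screening to first dose adds to this. The last column moves only the later visit to the earliest day that its printed window allows (3 days at weeks 5 and 13, 8 days at week 9).

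| Course | Week | Nominal start | Scheduled test before it | Minimum nominal age of result | With the visit at its earliest |
|---|---|---|---|---|---|
| 1 | 1 | day 1 | yes, pre-study | – | – |
| 2 | 5 | day 29 | none | 28 days | 28 − 3 = 25 days |
| 3 | 9 | day 57 | none | 56 days | 56 − 8 = 48 days |
| 4 | 13 | day 85 | none | 84 days | 84 − 3 = 81 days |

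**4. Effect of the fix.** Scheduled tests per woman of childbearing potential rise from 1 to 4, so 3 are added. The documents do not say how many such women will enroll; the Protocol Summary admits women over 18 and under 90. For the planned 28 patients the added assays therefore number between 0 and 3 × 28 = 84. This range describes cost and says nothing about risk.

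**The case against.** The strongest reply is that no rule is broken. Section 2.2.3 speaks of preventing pregnancy and of not dosing pregnant patients; it sets no retest interval. The plan acts on it with exclusion, contraception, an entry test and a ground for stopping treatment. Each course also begins with a physical exam, at which an investigator may order a test. The patients have metastatic disease and have already had chemotherapy fail, and the number who could conceive may be small or zero. All of this stands, and it limits the weight of the point. It does not supply a test: the exam can prompt one, but the plan does not ask for it.

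Four stronger readings are tempting and are not supported.

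- A reader might infer that the plan neglects pregnancy. It does not; the gap is confined to detection after entry.
- A reader might infer from the permissive verb in 5.7 that a woman known to be pregnant may continue on drug. The bullet's natural reading is drug off with follow-up continuing, and 2.2.3 says that pregnant patients should not be dosed. Firmer wording there would only clarify.
- A reader might note that 42 of 56 planned drug days (3 × 14 out of 4 × 14, or 75%) fall in courses with no scheduled test, and take this as a measure of risk. The share follows from having four equal courses and would be the same if no enrolled woman could conceive.
- A reader might infer that a pre-course test would catch most on-study pregnancies. No figure in the documents supports that. A very recent conception may test negative, and one that occurs during a course is exposed before the next test.

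One caution on cost also stands. The extracted calendar is misaligned in places, and its week 5 chemistry mark carries only the tumor-marker note. That blood is already drawn before each course therefore rests on the text of 5.3 item 2, not on the calendar.

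**Conclusion.** The gap is real and narrow. One pregnancy test is scheduled, before the study; three of the four courses start without one, when the screening result is nominally at least 28, 56 and 84 days old. Following the plan exactly permits dosing of an unrecognised pregnancy at a dose for which the protocol itself reports fetal harm in rats.

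The conclusion assumes that 5.2, 5.3 and 5.10 hold the complete assessment schedule. The consent pages were not in the text available, and they may say more to patients. The documents give neither a pregnancy rate nor the number of women of childbearing potential, so the absolute risk cannot be stated and may be low. No efficacy conclusion is affected. Because the potential harm is serious and the remedy is cheap, the change is worth making at the next amendment.

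**What to change.** In 5.3 item 2, add a serum pregnancy test for women of childbearing potential before each course after the first. Add matching marks at about weeks 5, 9 and 13 in the B-HCG row of 5.10. Run the test on the pre-cycle chemistry draw that 5.3 item 2 requires, and check that the calendar's chemistry row shows that draw at the same three visits. State that the course starts only after a negative result, and that drug is held while a positive result is confirmed.

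The cost is one added line, three calendar marks and up to three inexpensive assays per woman of childbearing potential. Where the pre-cycle draw is used there is no extra visit or needle. A course may wait briefly for a result or for confirmation of a positive. Sample size and endpoints are unchanged.

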2.2.4 Clinical Experience with LY2157299

To date, approximately 406 patients have been treated with LY2157299, with no definite drug-related toxicity profile emerging. The potential risks outlined in the Investigator's Brochure provided by Lilly are based upon the assumed mechanism of action for LY2157299 and the reported cases where LY2157299-associated toxicity was found to likely be the related cause due to lack of other contributing factors.

2.3 Rationale

Five years ago, Drs. [name], [name] and [name] argued for a revival of the notion of combining RT and IT in the treatment of cancer [45], the basic concept of this trial. The rationale is based on findings that radiation generates “danger” signals in tissues [46] that, under certain conditions, enhance immune presentation of tumor antigen liberated from radiation-damaged cells, thus working as a vaccine. This hypothesis stems from the ideas of Matzinger that the immune system is more concerned with responding to damage than to “foreignness” [47]. Radiation elicits damage signals, by up-regulating pro-inflammatory cytokines that are involved in DC maturation, immunomodulatory molecules such as major histocompatibility complex class I (MHC-I), co-stimulatory and adhesion molecules, death receptors of the tumor necrosis factor receptor (TNFR) family, and heat shock proteins (reviewed in [46]). [name]’s lab showed that irradiation of DC greatly enhances their ability to cross-present tumor antigen, a relevant immunological pathway during RT [48].

Increased production of TGF β has been found in many neoplasms such as breast, prostate, gastric, renal, and epidermal carcinomas, and elevated plasma TGF β levels in patients have been correlated with advanced disease, metastases, and lower survival rates [7-13]. TGF β can deactivate the anti-tumor defenses of the host by suppressing the immune system. With broad activity over natural killer (NK) cells, T cells, monocytes/macrophages, and dendritic cells, TGF β can affect the initiation and stimulation of both primary and secondary immune responses as well as suppress anti-tumor effector cells [20-25].

[name]’s lab and other groups have shown that ionizing radiation induces TGF β activation in vitro and in vivo in normal and cancer cells [49-55], which is at least in part occurring through a redox mechanism that acts directly on the secreted latent protein [56-57]. Moreover, TGF β is actually required for execution of the epithelial damage response to radiation [58-59]. [name] group made the surprising discovery that either genetic loss or pharmaceutical inhibition of TGF β inhibits ataxia telangiectasia mutated (ATM) kinase activity, thereby impeding the DNA damage response (DDR) and as a consequence, increasing radiation cell kill [59]. In addition, LY2109761, a similar compound to LY2157299 was evaluated in radiation-induced fibrosis models and showed a reversal of TGF- β -associated pro-inflammatory responses. This suggests that small molecule inhibitors of the TGF- β RI kinase may have a beneficial impact on TGF- β -mediated inflammation.

Recent studies underscore the growing concern that high TGF β levels in tumors drive cancer cells towards a more aggressive behavior and support their survival, while simultaneously limiting immune-responses by the host and, possibly, co-opting normal tissue functions like angiogenesis. Together with the recognition that radiation triggers activation of TGF β , which in turn promotes DNA damage repair, and mediates EMT [60] these results suggest a novel therapeutic advantage for TGF β inhibition in the context of radiotherapy.

